11.2.3. Phase 3 (Cohort 1)

Initial estimation

The sample size for phase 3 was initially estimated to be 1350 patients (150 patients per arm across 3 treatment arms in 3 cohorts). Based on the new endpoint of death or mechanical ventilation, the sample size for phase 3 has been re-estimated to be 2505 patients in each of cohort 1 and cohort 1A.

The study was planned to continue enrolling additional patients seamlessly into the phase 3 portion of the study, until an adaptation decision on the dose(s), primary endpoint and final sample size for phase 3 is made based on the phase 2 data analysis. A total sample size of approximately 5010 patients was estimated for the phase 3 portion of the study (2505 per cohort, 835 per arm across 3 treatment arms in 2 cohorts). For cohort 1, a total of 241 events (estimated sample size of 2505 patients [835 patients per arm]) would have been needed to provide 90% power at $\alpha=0.05$ (2-sided) using a log-rank test to detect a risk reduction of 35.8% (ie, HR=0.642) in the cumulative incidence of patients who died or went on mechanical ventilation, assuming a 12.5% cumulative incidence rate in the placebo group by day 29.

Final sample size

Finalization of the sample size and patient population for phase 3 was planned to be subject to change and would be determined after review of phase 2 data. However, enrollment of patients into the study was terminated prematurely by the Sponsor on 09 April 2021 because of extremely slow enrollment in the months preceding the decision. The sample size of phase 3 was not re-estimated.

Approximately 2252 patients were randomized in the study, which includes 60 patients in phase 1 cohort 1, 629 in phase 2 cohort 1, 755 in planned phase 3 cohort 1, 609 in phase 2 cohort 1A, 164 in phase 2 cohort 2 and 35 in phase 2 cohort 3.

Assuming the proportion of patients who died or went on mechanical ventilation from day 1 to day 29 in placebo group is 13.1% which is same as the blinded proportion in the Seronegative mFAS patients of the pooled phase 3 cohort 1 and phase 2 cohort 1A and alpha is 0.05 2-sided, the minimal significant difference in relative risk reduction between the REGN10933+REGN10987 2.4g and 8.0g combined dose group and placebo group is 29.0%, 41.2%, and 36.6% for overall mFAS, Seronegative mFAS, and High Viral Load mFAS patients, respectively.

11.3. Analysis Sets

11.3.1. Efficacy Analysis Sets

Full Analysis Set (FAS): The full analysis set (FAS) includes all randomized patients who received at least one dose (full or partial) of the study drug. Analysis of the FAS population will be done according to the treatment allocated (as randomized).

Modified Full Analysis Set (mFAS): The modified full analysis set (mFAS) includes all FAS patients with a positive SARS-CoV-2 RT-qPCR conducted in the central laboratory in NP swab samples at randomization and analysis is based on the treatment allocated (as randomized).

Seronegative mFAS: The seronegative mFAS is defined as all patients in mFAS with documented seronegative status at the baseline.

High Viral Load mFAS: The High Viral Load mFAS is defined as all patients in mFAS with baseline viral load $>10^6$ copies/mL.

Both FAS and mFAS will be used for the summaries of demographic and baseline characteristics and analysis of clinical/biomarker endpoints. The mFAS will be used for the analysis of all efficacy endpoints, based on the principle that an anti-viral agent would only be anticipated to provide efficacy in patients with measurable virus at baseline. The seronegative mFAS as well as the high viral load mFAS will be used for the primary analysis and descriptive analysis of certain virologic endpoints and clinical endpoints. Additional analyses will be performed in the seropositive mFAS, as needed.

11.3.2. Safety Analysis Set

The safety analysis set (SAF) includes all randomized patients who received a dose (full or partial) of the study drug. Analysis of the SAF will be done according to the treatment received (as treated). Determination of “as treated” will be based on the actual study drug received on day 1. Since the treatment of “as treated” is same as “as randomized” in this study, the FAS is equivalent to the SAF. Therefore, the treatment administration and all clinical safety variables will be analyzed using the FAS.

11.3.3. Pharmacokinetics Analysis Sets

The pharmacokinetics (PK) analysis population includes all patients who received any study drug of REGN10933 and REGN10987 and who had at least 1 non-missing drug concentration

measurement following the first dose of study drug as indicated in the Schedule of Events table. Patients will be analyzed based on actual treatment received.

11.3.4. Immunogenicity Analysis Sets

The ADA analysis set (AAS) includes all subjects who received any study drug (active or placebo) and at least one non-missing ADA result from the ADA assay after a first dose of the study drug or placebo.

The NAb analysis set (NAS) includes all treated subjects who received any study drug (active or placebo), have at least one non-missing ADA result following the first dose of study drug (active or placebo), and either tested negative at all ADA sampling times or tested positive for ADA with at least one non-missing NAb result after first dose of the study drug (active or placebo). Subjects who are ADA negative are set to negative in the NAb analysis set.

Subjects will be analyzed according to the treatment actually received.

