11.4.12. Analysis of Immunogenicity Data

Immunogenicity variables will be summarized using descriptive statistics.

Immunogenicity will be characterized by the ADA responses and titers observed in subjects in the ADA analysis set. ADA response categories and titer categories are defined as follows:

ADA response categories:

- ADA Negative, defined as ADA negative response in the ADA assay at all time points, regardless of any missing samples.
- Pre-existing immunoreactivity, defined as either an ADA positive response in the ADA assay at baseline with all post first dose ADA results negative, OR a positive response at baseline with all post first dose ADA responses less than 9-fold over baseline titer levels.
- Treatment-emergent response, defined as an ADA positive response in the ADA assay post first dose when baseline results are negative or missing. The treatment-emergent responses will be further characterized as Persistent, Indeterminate or Transient.
 - Persistent Response (only applicable to phase 1) – Treatment-emergent ADA positive response with two or more consecutive ADA positive sampling time points, separated by at least 16-week period (based on nominal sampling time), with no ADA negative samples in between, regardless of any missing samples.
 - Indeterminate Response –Treatment-emergent ADA positive response with only the last collected sample positive in the ADA assay, regardless of any missing samples.
 - Transient Response –Treatment-emergent ADA positive response that is not considered persistent or indeterminate, regardless of any missing samples.
- Treatment-boosted response, defined as a positive response in the ADA assay post first dose that is greater than or equal to 9-fold over baseline titer levels, when baseline results are positive.

Titer categories (Maximum titer values)

- Low (titer <1,000)
- Moderate (1,000 ≤ titer ≤ 10,000)
- High (titer >10,000)

The following analysis will be provided:

- Number (n) and percent (%) of ADA-negative subjects (pre-existing immunoreactivity or negative in the ADA assays at all time points) by treatment arms
- Number (n) and percent (%) of treatment-emergent ADA positive subjects by treatment arms and ADA titer categories

- Number (n) and percent (%) of persistent treatment-emergent ADA positive subjects
- Number (n) and percent (%) of indeterminate treatment-emergent ADA positive subjects
- Number (n) and percent (%) of transient treatment-emergent ADA positive subjects

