11.4.12.1. Analysis of Neutralizing Antibody Data

The absolute occurrence (n) and percent of subjects (%) with NAb status in the NAb analysis set will be provided by treatment groups.

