4.8. Immunogenicity Variables

The immunogenicity variables are ADA and (in phase 2 and phase 3 only) NAb status, titer, and time-point/visit. Serum samples for ADA will be collected at the visits as specified in Section 10.2. Samples positive in the ADA assay will be further characterized for ADA titers and for the presence of NAb.

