5.10.2. Immunogenicity and Safety and Efficacy

Potential association between immunogenicity variables and safety may be explored with a primary focus on the following safety events during the TEAE period:

- Infusion reactions
- Hypersensitivity (SMQ: Hypersensitivity [Narrow])
- Anaphylaxis (SMQ: Anaphylaxis [Narrow])

Potential association between immunogenicity variables and efficacy endpoints may be explored (e.g. scatter plot or spaghetti plot).

The safety and efficacy analyses mentioned above will be conducted using the following categories:

- ADA positive subjects: Subjects with treatment-emergent or treatment-boosted response.
- Maximum post-baseline titer.
- NAb positive

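### The NAb analysis set leaves out patients who are ADA-positive only at baseline, and it can count as NAb-positive some patients whom the ADA table counts as ADA-negative

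*Protocol*

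**What the plan says.** **Set membership.** Protocol 11.3.4, repeated in SAP 3.4, requires treatment, at least one post-dose ADA result, and that the subject "either tested negative at all ADA sampling times or tested positive for ADA with at least one non-missing NAb result after first dose".

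**Coding.** The same paragraph adds: "Subjects who are ADA negative are set to negative in the NAb analysis set".

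**Which samples are tested.** SAP 4.8: "Samples positive in the ADA assay will be further characterized for ADA titers and for the presence of NAb". The pre-dose sample is one of the ADA samples (Protocol 9.1.2.1, footnote 15).

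**ADA categories.** Protocol 11.4.12 and SAP 5.9.1 give the formal category: "ADA Negative, defined as ADA negative response in the ADA assay at all time points, regardless of any missing samples". Pre-existing immunoreactivity is a separate category with two forms. One is "an ADA positive response in the ADA assay at baseline with all post first dose ADA results negative". The other is a positive baseline with every post-dose response under 9-fold of the baseline titer.

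**ADA table.** The first planned count is of "ADA-negative subjects (pre-existing immunoreactivity or negative in the ADA assays at all time points) by treatment arms". Here both forms of pre-existing immunoreactivity are grouped with the negatives.

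**NAb output.** Protocol 11.4.12.1 and SAP 5.9.2 plan one summary: the number and "percent of subjects (%) with NAb status in the NAb analysis set will be provided by treatment groups".

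**Association analyses.** SAP 5.10.2 restricts one category: "ADA positive subjects: Subjects with treatment-emergent or treatment-boosted response". It also lists NAb positive, without that restriction.

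**The concern.** The membership rule has a condition for patients who are never ADA-positive and another for patients with a post-dose NAb result. Pre-existing immunoreactivity is a defined category in the same plan, and the rule does not handle it cleanly. One form drops out of the denominator although its post-dose status is known to be negative. The other form can enter the NAb numerator while the ADA table presents the same patients as ADA-negative.

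Immunogenicity measured by ADA and NAb is a listed secondary endpoint (Protocol 4.2), and its clinical consequences are named as an important potential risk (Protocol 3.3.2). A reader who sets the NAb table beside the ADA table would expect the two to reconcile. As written they need not. The NAb-positive group in any association analysis under SAP 5.10.2 could also include patients whom that section does not treat as ADA-positive.

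**Working it through.** The plan states no ADA prevalence, NAb rate or precision target for this analysis, so there is no figure to reproduce. The check follows each kind of patient through the rules and then applies assumed rates.

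**Step 1. Follow the patients through the rules**

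| ADA pattern | Negative at all sampling times? | Post-dose sample eligible for NAb testing? | In NAb set? | ADA table row |
|---|---|---|---|---|
| Never positive | Yes | No | Yes, set to negative | ADA-negative |
| Type A: baseline positive, all post-dose negative | No | No | **No** | ADA-negative |
| Type B: baseline positive, still positive post-dose, all under 9-fold | No | Yes | Yes, if a NAb result exists | ADA-negative |
| Treatment-emergent or boosted | No | Yes | Yes, if a NAb result exists | ADA-positive |

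The set-to-negative sentence does not bring type A back, because it codes members of the set and admits nobody.

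**Step 2. Coding of type B**

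- Narrow sense of *ADA negative* (the formal category, negative at all time points): type B is not set to negative, so a positive post-dose NAb result counts as NAb-positive.
- Broad sense (the ADA table row): type B would be set to negative whatever the assay showed.

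**Step 3. Size, under assumed rates**

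Let a be the share of the ADA set that is type A, b the share that is type B, f the fraction of type B with a positive post-dose NAb result, and t the share that is treatment-emergent or boosted and NAb-positive. Assume every other patient has the results needed for the set.

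- R1, rule as written, narrow sense: (t + b·f)/(1 − a)
- R2, rule as written, broad sense: t/(1 − a)
- R3, everyone kept, type B set to negative: t
- R4, everyone kept, measured NAb results used: t + b·f

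*Exclusion of type A alone.* R1/R4 = R2/R3 = 1/(1 − a), whatever the values of t, b and f. With t = 1%:

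| Assumed a | NAb % with type A kept (R3) | NAb % as written (R2) | Multiplier | Dropped, if all 2192 were evaluable |
|---|---|---|---|---|
| 1% | 1.00 | 1.01 | 1.01 | 22 |
| 3% | 1.00 | 1.03 | 1.03 | 66 |
| 5% | 1.00 | 1.05 | 1.05 | 110 |
| 10% | 1.00 | 1.11 | 1.11 | 219 |

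The 2192 is the phase 2/3 number randomized: 609 + 629 + 164 + 35 + 755. NAb is analyzed only in those phases (Protocol 11).

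*Type B.* The two senses differ by b·f/(1 − a). With t = 1%:

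- a = b = 1%, f = 25%: R1 = 1.25/0.99 = 1.26% and R2 = 1.01%.
- a = b = 5%, f = 50%: R1 = 3.5/0.95 = 3.68% and R2 = 1.05%. With everyone kept, R4 = 3.50% and R3 = 1.00%.
- f = 0: R1 = R2, so type B has no effect.

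The difference between R1 and R2 shows how much turns on the meaning of one term. It does not measure an error, because R4 is a legitimate count of post-dose NAb positivity.

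**The case against.** The strongest reply is that the planned NAb output is descriptive. It counts subjects by NAb status and is never called treatment-emergent, so including antibody that was present before dosing is not in itself an error. The set includes placebo patients and is reported by treatment group, so pre-existing NAb also shows in the comparator. ADA titers of patients with pre-existing responses are listed (Protocol 11.4.12, SAP 5.9.1). The association analyses in SAP 5.10.2 are ones that may be explored, and NAb is outside the testing hierarchy. All of this stands, and it sets the severity.

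A reader might go further and infer that the NAb rate is wrong however the text is read, or roughly doubled. The documents do not support either. Doubling appears only when any post-dose NAb positivity is compared with a treatment-related rate that the plan does not promise, and only with assumed inputs. The documents do not show that any such patient exists.

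A reader might also infer that measured NAb-positive results will be overwritten. That requires the broad sense of *ADA negative*, which appears only as a grouping inside one table row that spells out its own content. The coding sentence directly follows the condition of being negative throughout and matches the formal category, so the narrow sense is the natural one.

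The reply does not remove the exclusion of type A, which follows from the literal rule together with SAP 4.8. Nor does it remove the mismatch for type B, which arises on the natural reading.

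**Conclusion.** The concern holds in a limited form. As written, the NAb set excludes patients who are ADA-positive at baseline and negative at every post-dose sample, although they stay in the ADA set and the ADA table counts them as ADA-negative. The NAb percentage is inflated by 1/(1 − a), about 1.01 to 1.11 for an assumed a of 1% to 10%. Patients who stay positive below 9-fold can be counted NAb-positive, if their NAb result is positive, while the ADA table counts them as ADA-negative and SAP 5.10.2 does not treat them as ADA-positive.

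The exclusion rests on the literal membership rule and on NAb testing being confined to ADA-positive samples. The type B mismatch rests on the narrow sense of *ADA negative*. The actual size, and any difference between arms, cannot be obtained from the documents. Only descriptive immunogenicity output is affected and no hypothesis test changes. The severity is minor.

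**What to change.** In Protocol 11.3.4 and SAP 3.4:

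1. Admit to the NAb set patients who are ADA-positive at baseline with all post-dose ADA results negative, and code them NAb-negative.
2. State that *ADA negative* in the set-to-negative rule means no ADA-positive post-dose sample. No measured post-dose NAb result is then overwritten.

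In Protocol 11.4.12.1 and SAP 5.9.2:

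3. Report NAb results of patients with pre-existing immunoreactivity who remain positive below 9-fold on a separate row from treatment-emergent and treatment-boosted patients. Keep all of them in one common NAb-set denominator.

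In SAP 5.10.2:

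4. Make the same split for NAb positive in any association analysis that is run.

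The cost is a few sentences and one extra table row. No new samples or assays are needed.

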11.4. Statistical Methods

For continuous variables, descriptive statistics will include the following: the number of patients reflected in the calculation (n), mean, Q1, median, Q3, standard deviation (SD), minimum, and maximum.

For categorical or ordinal data, frequencies and percentages will be displayed for each category.

11.4.1. Demography and Baseline Characteristics

Demographic and baseline characteristics variables will be summarized by treatment group, and all groups combined. These will be analyzed for FAS and mFAS populations. Similar analysis will be performed by baseline serostatus and baseline viral load categories ($\leq 10^6$ copies/mL and $>10^6$ copies/mL) for mFAS population.

11.4.2. Medical History

Medical history will be summarized by SOC and PT and by treatment group and all groups combined in the mFAS and FAS population.

11.4.3. Prior / Concomitant Medications or Procedures

Prior or concomitant medications/procedures will be summarized by treatment groups. Summaries will present patient counts (and percentages) for all medications, dictionary coded by WHODRUG, by decreasing frequency of the overall group incidence (or high dose group incidence in tables where the overall is not presented) of ATC followed by ATC level 2, ATC level 4 and PT. Focus of the results will be on the list of targeted medications in the FAS and mFAS populations.

Number and proportion of patients undergoing a prior/concomitant procedure(s) will be summarized, sorted by decreasing frequency of SOC and PT based on the incidence in the overall group incidence (or high dose group incidence in tables where the overall is not presented). Patients will be counted only once for each SOC and PT linked to the procedure.

Prior or concomitant medications/procedures of interest for COVID-19 will be summarized similarly.

11.4.4. Patient Disposition

The following summaries will be provided for both mFAS and FAS populations.

- The total number of randomized patients: received a randomization number
- The total number of randomized patients who were not treated by study drug
- The total number of randomized patients who discontinued the study, and the reasons for discontinuation
- A summary of analysis sets including FAS, mFAS, SAF, PK, immunogenicity (ADA), and NAb analysis set (NAS)

11.4.5. Extent of Study Treatment Exposure

The following variables will be analyzed by treatment group:

- Duration of intravenous infusion
- Total volume of drug administered (units: mL)
- Number of patients with total planned dose administered (yes/no)
 - If no, reason for not administration of total planned dose (equipment failure, adverse event, other)
- Number of patients with infusion interruptions (ie, patients completed the full dose but had infusion interruptions)
- Number of patients with infusion discontinuation (ie, patients didn't completed the full dose infusion)

The number and percentage of patients randomized and exposed to double-blind study drug will be presented for each treatment group.

11.4.6. Efficacy Analyses

The efficacy analyses will be performed for the following patients on all efficacy endpoints, separately. The comparisons in all efficacy endpoints will be performed between the REGN10933+REGN10987 2.4g and 8.0g combined dose group and placebo group as well as between each treatment group and placebo group.

- Pooled phase 3 cohort 1 and phase 2 cohort 1A patients
- Phase 3 cohort 1 patients (ie, patients randomized after 01 December 2020 in cohort 1)
- Phase 2 cohort 1A patients

11.4.6.1. Primary Efficacy Analyses

11.4.6.2. Analysis of Primary Virologic Efficacy Endpoint

The primary analysis on the comparison between the REGN10933+REGN10987 2.4g and 8.0g combined dose group and placebo with respect to the virologic endpoint of time-weighted average daily change from baseline in viral load (\log_{10} copies/mL) from day 1 to day 7 and other post-baseline visit timepoint will be performed in the Seronegative mFAS in the pooled phase 3 cohort 1 and phase 2 cohort 1A patients. The estimand for the analysis is the difference in means between the REGN10933+REGN10987 2.4g and 8.0g combined dose group and placebo in the pooled phase 3 cohort 1 and phase 2 cohort 1A patients. Data collected after use of convalescent plasma therapy or other anti-spike monoclonals will be excluded from efficacy analysis. All other available data will be used in the analysis regardless of intercurrent events such as rescue medication or discontinuation, ie, treatment policy approach.

The analysis will be based on the observed data with no imputation for missing data except as defined in the SAP for viral load values that are below lower limit of detection (<LLOD), below lower limit of quantification (<LLOQ) or above upper limit of quantification (>ULOQ) of the assay.

The variable will be analyzed using the Analysis of Covariance (ANCOVA) model with treatment group and the type of background standard-of-care as fixed effects, and baseline viral load and treatment by baseline interaction as covariates.

The least squares means estimates for time-weighted average daily change from baseline in viral load for each treatment group, as well as the difference between the REGN10933+REGN10987 2.4g and 8.0g combined doses and placebo as well as between each individual dose treatment group and placebo, will be provided along with the corresponding two-sided p-value, standard error, and associated 95% confidence interval.

11.4.6.3. Analysis of Primary Clinical Efficacy Endpoints

The primary efficacy analysis will be the comparison between the REGN10933+REGN10987 2.4g and 8.0g combined dose group and placebo in the pooled phase 3 cohort 1 and phase 2 cohort 1A patients. The primary clinical endpoint defined in Section 4.1 will be analyzed using the landmark analysis approach for day 6 through day 29, as well as analyzed for day 1 through day 29 in the order specified in Section 11.4.9.

The proportion of patients who died or went on mechanical ventilation will be analyzed using either the exact method for binomial distribution or asymptotic normal approximation method. If the number of events is small (eg, $np \leq 5$ or $n(1-p) \leq 5$ in any treatment group, where n is the number of patients in the treatment group and p is the proportion of events), then the Fisher's exact test will be applied. Otherwise, stratified Cochran-Mantel Haenszel (CMH) test, stratified by the type of background standard-of-care (antiviral therapies and non-antiviral therapies), will be applied. Relative risk and relative risk reduction and corresponding 95% confidence intervals compared to placebo group will be estimated by Farrington-Manning method. Missing data will be considered as non-events.

The analysis will be performed for the High Viral Load mFAS, the Seronegative mFAS, and the overall mFAS.

